1. SYNOPSIS OF THE STUDY

SPONSOR	CHU de Toulouse
CO-ORDINATING/PRINCIPAL INVESTIGATOR	[name] Reference Centre for Prader-Willi Syndrome, Endocrinology Team / Hôpital des Enfants [Children's Hospital]/[name]/[contact]
TITLE	Evaluation of children aged from 3 to 4 years with Prader-Willi Syndrome who received OT between 0 and 6 months of age during the OTBB2 study and comparison with a group of untreated and age-matched children with PWS (OT2SUITE)
JUSTIFICATION / CONTEXT	PWS is a genetic developmental disorder affecting 1 child in 20,000 at birth, which combines neonatal hypotonia with a severe deficiency in the sucking reflex which may lead to a complete lack of weight gain. Currently diagnosis is made during the first weeks of life. In the absence of specific care and prevention, obesity then occurs in the 2nd year of life in association with other endocrine anomalies probably linked to hypothalamic dysfunction. An anomaly in the neurones secreting OT in the hypothalamic paraventricular nucleus is found both in patients and in 2 animal models (Necdin mice and MAGEL2 mice obtained after invalidation of these 2 genes situated in the PWS chromosomal region). Administration of OT during the first 5 hours of life in MAGEL2 mice allows the survival of 93% of pups as opposed to 51% without administration of OT, due to deficiency in the sucking reflex. Long-term effects are also found after early administration of OT, in particular the restoration of social behaviour in adult Magel 2 mice. In our previous OTBB2 study we carried out repeated intranasal administrations of OT for 7 days at different doses (4IU every 2 days, 4IU/day or 2x4IU/day) in babies with PWS aged less than 6 months. The tolerance of these administrations was excellent: no clinically significant anomaly in the different clinical and biological parameters monitored. Investigations have shown that out of the 18 babies included, 88% have normalised sucking/swallowing after the 7 days of treatment. Significant improvement in social skills is found, with increased eye contact, less withdrawal and intensified mother-baby interactions. Our results have also shown an increase in the levels of acylated ghrelin and changes in cerebral activity with increased connectivity of the right orbitofrontal cortex. These results will be published in the Pediatrics journal in February 2017. We have presented these very promising results to ANSM and EMA and both agencies have strongly recommended that we collect long-term data on these

OBJECTIVES	Main objective: to compare the communication skills of children with PWS aged between 3 and 4 years who have been treated for 7 days with OT in the OTBB2 study before the 6th month of life with untreated and age-matched children with PWS. Secondary objectives: To compare the group of treated children with PWS with the untreated group in terms of - adaptive behaviour, daily living skills, socialisation and motor skills - global behaviour - orality and eating behaviour - global development - evolution of height and weight and clinical condition - oculometric skills - cerebral activity - circulating rates of ghrelin and other peptides and neuropeptides involved in regulation of the appetite.
OUTLINE OF THE STUDY	Cross-sectional study of children with PWS comparing at the age of 3-4 years the behaviour and development of two groups of children with PWS treated or not with OT for 7 days during the first 6 months of life.
INCLUSION CRITERIA	 Male or female child with PWS (genetically confirmed diagnosis) Aged from 3 to 4 years The parents (or legal representative) must have signed the consent form and the child must be registered with a social security regime. For the treated group: The child has participated in the OTBB2 study. For the control group: The child has never received OT, agematched to children treated with OT by plus or minus 3 months.
EXCLUSION CRITERIA	- Administrative problems: inability to give parents (or legal representative) expert information, no coverage by a Social Security regime, refusal of parents (or legal representative) to sign the consent form.
OUTCOME MEASURES	Main criterion: Score in the "Communication" field of the Vineland II scale Secondary criteria: Scores in the fields "Daily living skills", "Socialisation" and "Motor skills", and the composite score for adaptive behaviour on the Vineland II scale Global behaviour (CBCL) Global development (BSID III) Evaluation of orality and eating behaviour (questionnaire, X-ray, clinical observation) Culometric tests Evolution of height and weight and clinical parameters Cerebral activity by functional MRI Circulating rates of ghrelin and certain peptides and neuropeptides involved in regulation of the appetite
STUDY SIZE	36 children: 18 children with PWS included in OTBB2 18 control children with PWS aged from 3 to 4 years and agematched to the treated children (plus or minus 3 months)

OT2SUITE V1.6 of 22/03/2017

EXPECTED NUMBER OF CENTRES	Monocentric
STUDY DURATION	Duration of inclusion period: 18mois Duration of participation of each patient: 3 days Total study duration: 24 months
STATISTICAL ANALYSIS OF DATA	Comparison of the 2 groups of children with regard to the studied criteria: communication, adaptive behaviour, global behaviour, eating behaviour and orality, global development, oculometric skills, cerebral activity, circulating rates of ghrelin and other neuropeptides
EXPECTED OUTCOMES	If positive effects on communication skills, eating behaviour, development and social skills in children with PWS aged between 2 and 4 years who have received early intranasal administration of OT are demonstrated with good tolerance, we will document the long-term effect of OT administered during the first months of life to babies with PWS and its modifying action on the natural history of the disease.

2. ABSTRACT

This research has been registered in http://www.clinicaltrials.gov/ the *date* under the n° *numéro*.

Long term evaluation of infants aged from 3 to 4 years old included in the OTBB2 study (repeated administrations of oxytocin in infants with PWS aged from 0 to 6 months) and comparison with not treated and age-matched PWS infants (OT2SUITE)

Follow-up of PWS infants treated by oxytocin and comparison with not-treated infants.

Sponsor of this research. CHU Toulouse

Background: In our previous OTBB2 study, 18 infants with PWS aged from 0 to 6 months received intranasal administrations of oxytocin (4 UI every 2 days, 4UI every day or 2x4UI every day during 7 days). Tolerance of oxytocin was excellent. Sucking assessed by the neonatal oral motor scale (NOMAS) was abnormal in all infants at baseline and normalized in 88%. Significant improvements in Clinical Global Impression scale, social withdrawal behavior and mother-infant interactions were observed. We also documented a significant increase in acylated ghrelin and connectivity of the right superior orbitofrontal network that correlated with changes in sucking and behavior.

Purpose:

In accordance with recommendations of regulatory authorities (EMA and ANSM), we want to collect long term data of patients treated with oxytocin before the age of 6 months. Morover clinical observations of these infants support long term effects on communication skills, global development and behaviour. The objective of this study is to collect data on tolerance and effects of early treatment with oxytocin in infants with PWS aged from 3 to 4 years and to compare these infants with not treated age-matched infants with PWS.

- **Primary outcome:** Evaluation of communication skills assessed by Vineland-II scale.
- Secondary outcomes:

Evaluation of:

- o Adaptative behavior composite and 3 domains: "Daily living skills", "Socialization", "Motor skills" (Vineland-II scale).
- o Behavioral troubles (CBCL questionnaire)
- o Global development (BSID III questionnaire)
- o Orality and eating behaviour (questionnaire, videofluoroscopy of swallowing, clinical observation)Eye tracking abilitiesAuxological and clinical parameters
- o Brain activity (fMRI bold)
- o Plasma levels of ghrelin and other peptides involved in feeding behaviour or energy metabolism
- **Study design**: comparison of 2 groups of infants with PWS: infants treated with oxytoxin at the age of 0-6 months and age-matched infants not treated
- Eligibility criteria:
 - inclusion criteria:
 - infants with PWS (genetic diagnosis confirmed)
 - aged from 3 to 4 years
 - For treated group: infant included in the OTBB2 study
 - For not treated group: infant never treated with OT
 - exclusion criteria: none
- **Arm number or label and arm type**: 2 groups of infants with PWS: infants treated with oxytoxin at the age of 0-6 months and age-matched infants not treated
- **Interventions**: not applicable
- Number of subjects: 18 infants treated with oxytocin at the age of 0-6 months and 18 infants not treated
- **Statistical analysis**: description of variables in the oxytocin treated group and comparison between the treated and the age-matched not treated group by Mann-Witney test for continuous variables and by Fisher's test for nominal variables.
- **Key-words:** Prader-Willi, oxytocin, communication skills, oral skills, brain activity.

3. SCIENTIFIC JUSTIFICATION AND GENERAL DESCRIPTION

3.1. CURRENT STATE OF KNOWLEDGE

3.1.1. REGARDING THE PATHOLOGY

Prader-Willi Syndrome (PWS) is a rare genetic developmental disease (1/20,000 births) linked to the lack of expression of genes of paternal origin (parental imprinting) situated on chromosome 15 in the region q11-q12. For about ten years, due to the early diagnosis (1st month of life), the natural history of the disease has been well described, in particular the various nutritional phases (Miller *et al.*, 2011).

These children all present severe neonatal hypotonia and difficulties with sucking/swallowing which can lead to a severe deficit in weight gain, justifying nutrition by naso-gastric tube in 80% of cases, followed by an improvement in food intake (Miller *et al.*, 2011). A phase of weight increase without increase in food intake appears at around 2 years of age. Secondarily, after the age of 3 years, patients undergo excessive weight gain and develop increased interest in food along with significant anxiety and behavioural problems (Goldstone *et al.*, 2012, Miller *et al.*, 2011). In the absence of treatment, severe obesity appears with hyperphagia and lack of satiety together with aggravation of behavioural problems, constituting the classic profile of the disease (Goldstone *et al.*, 2012, Miller *et al.*, 2011). The physiopathological mechanism explaining the transition between anorexia and severe obesity has not yet been explained. Hyperphagia and behavioural troubles, which are consistent in these patients, have a large impact on their daily life and that of their families and hinder their socialisation (Dykens *et al.*, 2011). Moreover, these patients present endocrine deficiencies, partly linked to dysfunction of the hypothalamus, requiring hormone supplementation. At the psychiatric level, autistic spectrum characteristics and severe anxiety are often associated with mood disorders.

Patients with Prader-Willi Syndrome present communication disorders from birth. Then during childhood and adulthood they present mild or moderate intellectual impairment, attention deficit, dysfunction of executive functions, and also communication disorders, problems with social skills, emotional and linguistic disorders. One recent study showed that children with PWS have more somatic problems, difficulties in social interactions, problems with train of thought and signs of withdrawal/depression compared to age-matched control groups (Skokauskas *et al.*, 2012). The authors also specified that cut-off scores were found for the affective and somatic domain and attention deficit/hyperactivity. This complex combination of somatic, psychiatric and behavioural problems cause severe consequences for patients, their parents and family. Due to their early lack of interaction and social engagement, children with PWS do not benefit as much from the experience of daily audiovisual exposure to communicating faces in comparison with children without PWS. This can dramatically impact their skills at integrating and interpreting the acoustic and visual signals which may contribute to their socio-cognitive immaturity later in their development.

We have demonstrated a deficit in audiovisual integration and discrimination of the human voice in PWS adults in a collaborative study with a team from the brain and cognition research centre (Salles *et al.*, 2016).

3.1.1. REGARDING REFERENCE PROCEDURES AND THOSE UNDER REVIEW

OT and behaviour:

Oxytocin (OT) is a nonapeptide synthesized in the paraventricular and supraoptic nuclei of the hypothalamus and is secreted into the blood system via axonal projections in the posterior lobe of the pituitary gland. The

peripheral actions of OT are well known on the triggering of labour and the stimulation and maintenance of breast feeding. In addition, OT also acts as a neuromodulator/neurotransmitter in the central nervous system, essentially via a dendritic secretion. In addition, its anorectic effect by controlling satiety has been known for several years. The central actions of OT and the peptide of the same family, arginine vasopressin or AVP, have more recently been implicated in social recognition, social memory, the attachment process (formation of the mother/child bond and intimate relationships, distress caused by separation and other aspects of social attachment) (Kosfeld *et al.*, 2005). Finally, OT has also been implicated in the regulation of the response to stress (Lischke *et al.*, 2012), and intranasal administration of OT has allowed improvement in the quality of eye contact in children with fragile X syndrome (Hall *et al.*, 2012) and in children with autistic spectrum disorders (Guastella *et al.*, 2010) in this latter case with contradictory results depending on the studies.

OT and eating behaviour:

It has been demonstrated in adult rats that OT administered intraventricularly or intraperitoneally induces a dose-dependent inhibition of nutrition (reduction of the quantity ingested, decrease in the duration of feeding, prolongation of the period of fasting) and an inhibition of the ingestion of water. In contrast, intraventricular injection of an OT antagonist results in increased appetite and prevents the anti-dipsogenic effect of OT (Arletti *et al.*, 1990). The central oxytocinergic projections appear to play a role in the control of consumption of sugary foods (Amico *et al.*, 2005, Billings *et al.*, 2006). Moreover, central OT appears to participate in limiting the ingestion of unknown foods and limiting the ingestion of appetising, sweet foods.

OT and murine PWS model:

In collaboration with the team of [name], we demonstrated that in knockout mice for the gene Magel2 located in the chromosomal region of PWS, which represent a good model of PWS, 50% of new-born mice died spontaneously in the first hours of life due to lack of effective suckling. A single administration of OT in the window of the first 5 hours of life restores suckling activity and allows the survival of 100% of new-born mice (Schaller *et al.*, 2010) and in the longer term in adult mice, normalises learning problems, memory and social behaviour (Meziane *et al.*, 2015).

The effect of OT on the stimulation of suckling observed at birth in knockout MAGEL2 mice thus appears different and novel from this point of view. However, recent data implicating the collaboration between OT and endocannabinoids in the hypothalamus and more specifically the supraoptic and paraventricular nucleus (McDonald *et al.*, 2008) may explain the important role of OT in suckling. Moreover, OT is implicated in early mother-child interactions and in the process of attachment.

OT in Prader-Willi Syndrome:

In 1995, Swaab et col. reported a deficit in the number and volume of neurons in the paraventricular nuclei of the hypothalamus which secrete OT in the brain of patients with PWS (Swaab *et al.*, 1995). A functional decrease in expression of the OT receptor gene was shown by Bittel et col (Bittel *et al.*, 2007). Our hypothesis is that in PWS, the lack of OT could explain both the difficulties with suckling observed at birth and, in the

longer term, the problems linked to the lack of early establishment of the circuits for regulating the appetite and certain behavioural problems.

Thus we carried out a phase I/II proof-of-concept study in infants with PWS aged under 6 months. 18 infants from all over France were included from May 2013 to July 2014 in the paediatric endocrinology department of CHU de Toulouse. During this study they received OT intranasally for 7 days, in 3 stages: 4 IU every 2 days (N=6), 4 IU per day (N=6) or 4 IU twice per day (N=6).

We evaluated the tolerance and the effects on eating behaviour and in particular sucking/swallowing, social skills by clinical observations and videos rated blindly by independent third-parties, as well as the circulating rates of acylated and non-acylated ghrelin and measurements of cerebral connectivity evaluated by fMRI.

The results show excellent tolerance with no undesirable effects or arginine-vasopressin-like effects associated with an excess of OT. No dose-related effect was observed. Sucking/swallowing was abnormal in all infants at inclusion and was normalised in 88% of the children after the 7 days of treatment; this improvement was shown by a significant reduction from 16 to 9 (p<0.001) in the scores on the NOMAS scale (neonatal oral motor scale) and from 18 to 12.5 (p<0.001) in the videofluoroscopic swallowing scores. We demonstrated a significant improvement in the clinical global impression (CGI), of the [social] withdrawal of the child (Alarm Distress BaBy scale), and in mother-child interactions (Coding Interactive Behaviour scale). We have also documented a significant increase in acylated ghrelin and in the connectivity of the upper right orbitofrontal network which are correlated to changes in sucking and behaviour. These key results are detailed in the article recently accepted for publication in Pediatrics and will appear in February (Appendix I).

It is necessary to evaluate the long-term effects to determine whether and how OT changes the course of the disorder.

Moreover, these promising effects must be confirmed by a phase III study which will begin during 2017 and for which we have already obtained financing from PHRC in 2015.

3.2. RESEARCH HYPOTHESES AND EXPECTED RESULTS

We have presented the very promising results of the OTBB2 study to ANSM and EMA and both agencies have strongly recommended that we collect long-term data on these patients treated before the age of 6 months.

The OTBB2 study has made it possible to show the major effects of OT on infants with PWS: on the global clinical status of the patient, eating behaviour, social skills, cerebral connectivity and circulating levels of ghrelin.

These early effects of the administration of oxytocin persist for 3 weeks after the last administration and clinical observations of the children monitored at the centre of reference in Toulouse support a long-term effect. The 18 treated children appear to have better social skills, better psychomotor development and earlier establishment of the prerequisites for communication compared with the children with PWS who were not treated. These observations are consistent with the results reported in Magel2 mice which demonstrate that early administration of OT normalises learning, memory and social skills in the adult mice. Moreover, functional modifications have been observed after treatment with oxytocin in these infants.

In accordance with the request of the agencies, we hope to re-evaluate the 18 children treated in the OTBB2 protocol and compare them to a control group of children with PWS who have never been treated with OT. The comparison will focus on communication skills, adaptive behaviour, global behaviour, orality and eating behaviour, global development, evolution of height and weight and clinical parameters, oculometric skills, cerebral activity and circulating rates of peptides implicated in eating behaviour.

The control group will consist of 18 children with PWS aged between 3 and 4 years, age-matched to the experimental group, seen at the reference centre for evaluation and/or routine monitoring.

3.3. RISK/BENEFIT BALANCE

The risks linked to participation in this study are:

- The risk linked to X-rays is low because with current methods the irradiation is 20 μGray which is far lower than 1 non-digital chest X-ray.
- There is currently no known risk linked to MRI examination other than the standard contraindications. Patients with PWS routinely have cerebral imaging carried out generally after 2 years. There is no need for anaesthesia or sedation. MRI examinations have already been performed by our team on patients with PWS with no major difficulty in the vast majority of cases.

It is important to note that all these examinations are likely to be carried out as part of the care of the children with PWS at the Reference Centre.

- For the oculometric assessment, no undesirable effect is expected with the eye-tracking system, a non-ionising and non-invasive technique. The infra-red light emitted by the eye tracker (TOBI) is not harmful to the human eye.

Taking account of the minimal risks incurred by the subjects, the risk/benefit balance for the children with PWS can be considered acceptable for this study. The benefit is above all collective: if an improvement is observed in the long-term state of health of the children with PWS treated with OT during their first 6 months of life, this will document our hypothesis of a positive long-term effect and will support our request for market authorisation in the near future, so that all babies with PWS can be treated.

3.4. EXPECTED OUTCOMES

If the safety and long-term effects (between 2 and 4 years) of early and repeated intranasal administration of OT are demonstrated, we will be in a favourable position to begin our next phase III study with a view to obtaining the MA for oxytocin in Prader-Willi Syndrome.

4. OBJECTIVES OF THE STUDY

4.1. MAIN OBJECTIVE

The main objective is to compare the communication skills of children with PWS aged between 3 and 4 years who have been treated for 7 days with OT before their 6th month of life in the OTBB2 study with untreated and age-matched children with PWS.

4.2. SECONDARY OBJECTIVES

The secondary objectives are to compare the group of treated children with PWS with the group of untreated children in terms of:

- adaptive behaviour, daily living skills, socialisation and motor skills
- global behaviour
- orality and eating behaviour
- global development
- evolution of height and weight and clinical condition
- oculometric skills
- cerebral activity
- circulating rates of ghrelin and other peptides and neuropeptides involved in regulation of the appetite
 (leptin, cortisol, insulin, GLP-1, PYY, pancreatic polypeptide, orexin A, αMSH).

5. OUTLINE OF THE STUDY

A cross-sectional biomedical study comparing at the age of 3-4 years the behaviour and development of two groups of children with PWS treated or not with OT for 7 days during the first 6 months of life. This national, mono-centric study will take place at CHU de Toulouse Purpan.

6. ELIGIBILITY CRITERIA

6.1. INCLUSION CRITERIA

The OTBB2 study finished in July 2014 and it was possible to include 18 babies who were seen regularly at the reference centre; all the children included in OTBB2 will be offered the study. This will be the treated group.

For the treated group:

- Male or female child with PWS (genetically confirmed diagnosis) who has participated in the OTBB2 study (i.e. has received intranasal administrations of OT for 7 days before the age of 6 months), aged from 3 to 4 years at the time of inclusion.

For the untreated control group:

- Male or female child with PWS (genetically confirmed diagnosis) aged from 3 to 4 years at the time of inclusion and never treated with OT, age-matched to the children treated with OT plus or minus 3 months.

The parents (or legal representative) must have signed the consent form and the child must be registered with a social security regime.

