6.3. RECRUITMENT METHODS

For the group of children treated with OT:

The team from the reference centre will contact the families. There should not be any patients lost to follow-up, given that the patients who participated in the OTBB2 study and treated with OT are regularly monitored as part of their normal care by the PWS Centre of Reference at CHU de Toulouse.

For the control group of untreated children:

[figure not shown]
Since treatment with OT is not authorised, no child with PWS currently benefits from this treatment. For the group of control patients, the team at the reference centre will present the study by telephone to the families whose children meet the inclusion criteria ahead of a planned hospital stay at the reference centre. They will be included after the signature of the informed consent form by the parents or legal representative. Approximately 40 children with PWS are born in France every year. The inclusion period of 18 months will therefore be sufficient to include the 18 patients planned in this group.

After an adequate reflection period (between 2 and 10 days), if the parents agree to participate in this protocol they will contact one of the investigators at the reference centre who will organise the inclusion visit at CHU de Toulouse. The children will be hospitalised at CHU de Toulouse in the PWS reference centre, only one parent may sleep in the room with the child, the other may be accommodated in a suitable facility close to the Children's Hospital.

We will also explain to the family that, with some exceptions, participation in the study will not extend the duration of hospitalisation of these children for the routine assessments carried out, which is generally 3 days. The study will thus be carried out during a routine hospital stay in the reference centre.

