7. STRATEGY OF THE STUDY

7.1. STRATEGY OF THE STUDY

7.2. COMPARISON STRATEGY

In the 18 babies included in the OTBB2 study we have not observed a serious adverse effect linked to OT. These children appear to have improved from the point of view of behaviour, development, communication and social skills. We wish to compare them to a control group of children with PWS not treated with OT, agematched and monitored in a comparable manner at the reference centre in order to analyse the long-term effect of OT. This strategy will allow us to document the modifying effect of early treatment with OT on the course of the disease.

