Oxytocin (OXT) is a neuropeptide that plays an important role in modulating social interactions and mother-infant bonding (Alves et al., 2015, Carson et al., 2013, Carter, 2014, Insel, 2010, Numan and Young, 2015). Quantitative neuroanatomical studies of post-mortem human hypothalamic tissue from patients with Prader-Willi syndrome (PWS) have demonstrated a reduced number and volume of OXT neurons in the paraventricular nucleus in comparison with controls (Swaab et al., 1995). Similarly, an alteration in the OXT system was described in PWS mice models (Schaller et al., 2010). Interestingly a single OXT injection before the first 5 hours of life, rescued 100% of the newborn Magel2 KO mice from early death by restoring normal sucking activity (Schaller et al., 2010). Magel2 KO mouse is now considered as a mouse model for PWS and autism spectrum disorder (ASD) as truncated mutations in Magel2 gene have been reported in some patients with ASD (Schaaf et al., 2013) Restricted production of mature OXT despite normal prohormone production was detected specifically in the hypothalamus of the Magel2 KO pups. Altogether these data suggest that OXT is involved in the pathophysiology of PWS and ASD12.

PWS is a rare complex genetic neurodevelopmental disease comprising several nutritional phases (Goldstone et al., 2008, Miller et al., 2011). From birth to 9 months infants with PWS display severe hypotonia, poor interactions and anorexic behavior with poor suck that may cause life-threatening complications like aspiration. Nasogastric tube feeding (NGT) is started at birth in more than 80% of the infants to ensure normal weight gain (Bachere et al., 2008).

Genetic diagnosis which is now made in the first months of life (Goldstone et al., 2008) offers a unique opportunity for early treatment with OXT. We report here the results of a proof-of-concept phase I/II

study of a short course of intranasal OXT (7 days) in 18 infants with PWS under 6 months old on safety, feeding and social skills, ghrelin levels and brain connectivity.

Methods

Patients: Eighteen infants with a genetic diagnosis of PWS were recruited and hospitalized in our French reference center for PWS with the presence of at least one parent. A detailed description of the population is shown in Table 1.

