In addition, after OXT treatment the infants displayed an increased interest in food that may have been related to the observed increase in circulating AG, called "the hunger hormone" as it is the only known orexigenic hormone(Cabral et al., 2015). Indeed we have data showing that AG is lower in infants with PWS compared with controls and OXT treatment seems to normalize it (data not shown). Importantly, we document the positive effects of OXT treatment on behavior and social engagement and on mother-infant interactions. After OXT, the infants were more alert, less fatigable, more expressive, and have less social withdrawal. They initiated mutual activities and, were more engaged in relationship through gaze, behavior and vocalizations. These modifications helped the parents to be more sensitive. The dyad was less restricted and there was a better reciprocal exchange, thus engaging the dyad in a positive transactional spiral as well as optimizing feeding. This improvement was also reported by infant observation in gaze, holding and handling. In humans, "mutual gaze" is the most fundamental manifestation of social attachment (Carter, 2014). Indeed we are aware that these changes may have been due to OXT and/or to the support and guidance provided by the expert team to the parents. Interestingly, similar improvement in parent-infant interactions was reported when OXT was given to the parent (Weisman et al., 2013).

Importantly, these early effects of OXT persisted 3 weeks after the last OXT administration and we have now preliminary data supporting the long-lasting effects one year after the end of the study on feeding, behavior and social skills in 16 infants. This is in line with the results reported in the Magel2 deficient mice showing that a short course of early treatment with OXT in pups rescued feeding at birth and had late effects normalizing learning, memory and social cues in adult males (Meziane et al., 2015). In addition, anatomical and functional modifications of the brain OXT-system were partly restored by OXT treatment (Meziane et al., 2015).

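### The control criteria in section 6.1 do not require the early diagnosis and early reference-centre care that every treated child had by entering OTBB2

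*Protocol*

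**What the plan says.** **Treated group.** Section 6.1 requires participation in OTBB2, meaning that the child "has received intranasal administrations of OT for 7 days before the age of 6 months". The OTBB2 article in Appendix 1 (Methods) describes the entry route: "Eighteen infants with a genetic diagnosis of PWS were recruited and hospitalized in our French reference center for PWS", all under 6 months old. Section 6.1 adds that these were "18 babies who were seen regularly at the reference centre".

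**Control group.** Section 6.1 asks for genetically confirmed PWS in a child "aged from 3 to 4 years at the time of inclusion and never treated with OT", within 3 months of age of the treated children. Section 6.2 adds only administrative exclusions and concurrent studies. Section 6.3 recruits by telephone among "families whose children meet the inclusion criteria ahead of a planned hospital stay at the reference centre".

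**Comparability.** Section 7.2 describes the controls as "monitored in a comparable manner at the reference centre in order to analyse the long-term effect of OT". Section 3.2 is looser: controls are children "seen at the reference centre for evaluation and/or routine monitoring".

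**Analysis.** Section 12.2 names a Student or Mann-Whitney test for scores and Fisher's exact test for categorical variables. It mentions no adjustment.

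**The concern.** The two groups enter by different doors. Entry to OTBB2 needed a genetic diagnosis, a referral and a stay at the expert centre in the first 6 months of life. Entry as a control needs a planned stay at that centre at age 3 to 4. A child first diagnosed or first referred at 2 years meets every control criterion and could never have been an OTBB2 participant.

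This matters because early expert support is a rival explanation that the OTBB2 investigators themselves raise. The Discussion in Appendix 1 says that "these changes may have been due to OXT and/or to the support and guidance provided by the expert team". If that support comes early for all treated children and for only some controls, an unadjusted comparison of Vineland-II Communication scores mixes its effect with that of oxytocin. Section 7.2 intends the comparison to show that early oxytocin modifies the course of the disease, and section 3.3 would use a favourable result to support a marketing request.

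**Working it through.** **1. The plan's own figure.** Inputs from section 12.1: two-sided test, alpha 5%, power 80%, difference 15 points, SD 15 in both groups, ratio 1. The noncentral-t calculation gives power of 78.1% with 16 per group, 80.7% with 17 and 83.0% with 18. The stated 17 per group is reproduced. The sample size is not in dispute.

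**2. What each group is guaranteed.**

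| Feature | Treated | Control |
|---|---|---|
| Genetic confirmation of PWS | yes | yes |
| Diagnosis before 6 months | yes, through OTBB2 entry | not required |
| Stay at the reference centre before 6 months | yes, through OTBB2 entry | not required |
| Contact with the centre at 3 to 4 years | yes | yes |
| Current age | 3 to 4 years | 3 to 4 years, matched within 3 months |

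Current age is the only matching factor. The statement in section 7.2 gives no age at which comparable monitoring must have begun, and nothing in section 6 turns it into a rule.

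**3. Illustration of size.** Let f be the share of controls with late diagnosis or late referral, and D their mean deficit in Communication points. Neither is in the documents; both are assumptions.

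- Expected bias = f x D.
- Standard error of the difference = 15 x sqrt(2/18) = 5.0 points; the 95% half-width is 10.2 points.
- 100,000 simulated t-tests per case, 18 against 18, SD 15, no oxytocin effect, with each control carrying the deficit D with probability f.

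| f | D | Bias (f x D) | Two-sided false-positive rate | Of which favouring oxytocin |
|---|---|---|---|---|
| 10% | 5 | 0.5 | 5.0% | 3.1% |
| 10% | 10 | 1.0 | 5.4% | 3.8% |
| 10% | 15 | 1.5 | 5.8% | 4.6% |
| 25% | 15 | 3.75 | 10.5% | 10.1% |
| 50% | 15 | 7.5 | 28.1% | 28.0% |

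The nominal rates are 5% and 2.5%. The 10% rows fit the protocol's account of early diagnosis best. The last two rows show only how the figure grows; no passage supports shares that large.

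**4. Which route is likelier.** The synopsis places diagnosis in the first weeks of life, section 3.1.1 in the first month, and the Appendix 1 introduction in the first months. Late diagnosis is therefore probably uncommon. None of these passages says when a diagnosed child first reaches the Toulouse centre, so late referral is the likelier route.

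**The case against.** The case on the other side is substantial, and much of it stands.

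- **Size.** A reader might take the 14.52-point gap in section 12.1 (79.57 - 65.05) as the cost of late diagnosis and derive biases of several points. The documents do not support this. The gap is between two groups aged 4 to 21 in a publication that section 9.1 describes as concerning growth hormone. Nothing ties it to age at diagnosis or referral.
- **Growth hormone.** It should not be counted as an advantage of the treated group. Section 8 describes its start in the second semester of life as general practice and says that OTBB2 children also followed recommendations.
- **Controls seen only once.** Section 3.2 invites that inference, but sections 6.3 and 10.4 place the study in a routine stay for normal follow-up. The open question is when that follow-up began.
- **Direction.** A reader might conclude that the bias must favour oxytocin. No passage shows lower Communication scores in late-diagnosed or late-referred children, and late recognition could reflect milder early signs. The admission in Appendix 1 concerns short-term change around a 7-day treatment, not Vineland-II scores at 3 to 4 years.
- **Status.** Section 12.2 calls the analyses mainly exploratory, section 3.1.1 announces a phase III study, and a SAP not at hand may adjust for covariates.

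These points limit the size and certainty of the bias. They do not close the gap: eligibility is fixed in the protocol, and adjustment helps only if the ages are recorded and the groups overlap on them.

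**Conclusion.** The point holds as a gap in control eligibility with a modest and uncertain consequence. Section 6.1 guarantees early diagnosis and early expert care in the treated group only, and the comparability asserted in section 7.2 is not enforced by any criterion. A bias in favour of oxytocin is plausible but inferred. Under the assumption that 10% of controls carry a deficit of 5 to 15 points, it is 0.5 to 1.5 points, small beside the 15-point target and the 10.2-point half-width, with a false-positive rate of about 5 to 6%. Larger shares would give more, but the documents neither supply nor suggest them. The change is worth making because it is cheap and removes one clear route of non-comparability; the documents do not show that the comparison is invalid without it.

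**What to change.** 1. Add to the control criteria in section 6.1: *genetic diagnosis confirmed before 6 months of age according to the medical file*. A broader rule, that the control would have qualified for OTBB2, cannot be written from this document because the full OTBB2 entry criteria are not given.
2. Record age at diagnosis and age at first reference-centre care in both groups, and compare them.
3. Add a sensitivity analysis of the primary outcome limited to, or adjusted for, early reference-centre care.
4. In section 6.3, approach eligible control families consecutively and log refusals.
5. Reconcile sections 3.2, 6.1 and 7.2 on how controls are followed.

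**Cost.** A short amendment, a check of existing files and two extra dates per child. The requirement of 17 per group is unchanged. The control pool becomes somewhat smaller; on the protocol's own account of early diagnosis, the first criterion should exclude few children. The number available at Toulouse is not stated: the figure of about 40 births a year in section 6.3 is for all of France, so multiplying it up does not show that the pool is ample. For that reason early reference-centre care is better handled in the analysis than made a strict criterion.
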